7.3 Laboratory tests

Laboratory analyses are based on data received from the central laboratory. Laboratory data will be converted into SI units. Unless noted otherwise, summaries and listings will include scheduled, re-test and unscheduled assessments.

Descriptive summary statistics for each scheduled visit (re-test excluded) will be provided for observed values and change from baseline in both hematology and blood chemistry laboratory parameters.

The change from baseline to last value (re-test and unscheduled assessments excluded) in the DB study period for hematology and blood chemistry parameters will be summarized.

Marked laboratory abnormalities are defined in [Table 4](#) below. The number (%) of subjects with marked laboratory abnormalities during DB study treatment will be tabulated. A subject will be counted only once, but may be reported in more than one marked laboratory abnormality criterion of a given parameter. Percentages will be based on the number of subjects at risk, i.e., those having at least one post-baseline value for a given parameter.

Shift from baseline to worst value post-baseline based on laboratory normal ranges will be provided for the following laboratory parameters:

- Liver enzymes: alanine aminotransferase (ALT), aspartate aminotransferase (AST), gamma-glutamyl transferase and total bilirubin (TBIL).
- Thyroid hormones: Thyroid-stimulating hormone, free T₃ and free T₄.
- Lipids: total cholesterol and triglycerides.
- Hematology: leukocytes, neutrophils, lymphocytes, eosinophils.

All laboratory data for subjects with at least one marked laboratory abnormality during DB study treatment will be listed. Any local laboratory data collected will be listed separately.

Table 4 Marked abnormalities in laboratory parameters for reporting

Laboratory parameter	Criteria for marked laboratory abnormalities
Hematology (SI unit)	
Hemoglobin (g/L)	< 100 < 80 > 20 above ULN or > 20 above baseline if baseline > ULN > 40 above ULN or > 40 above baseline if baseline > ULN
Hematocrit (%)	< 32% (Male); < 28% (Female) < 20% > 60% (Male); > 55% (Female) > 65%
Platelets (10 ⁹ /L)	< 75 < 50 > 600 > 999
Leukocytes (10 ⁹ /L)	< 3.0 < 2.0

Laboratory parameter	Criteria for marked laboratory abnormalities
	> 20.0 > 100.0
Neutrophils (10 ⁹ /L)	< 1.5 < 1.0
Eosinophils (10 ⁹ /L)	> 5.0
Eosinophils (%)	> 5%
Lymphocytes (10 ⁹ /L)	< 0.8 < 0.5 > 4.0 > 20.0
Reticulocyte (%)	> 2.5%
Blood chemistry (SI unit)	
ALT (U/L)	> 3 × ULN > 5 × ULN > 10 × ULN
AST (U/L)	> 3 × ULN > 5 × ULN > 10 × ULN
Alkaline phosphatase (U/L)	> 2.5 × ULN > 5 × ULN
Total bilirubin (µmol/L)	> 2 × ULN > 5 × ULN
Creatinine (µmol/L)	> 1.5 × ULN or > 1.5 × baseline if baseline > ULN > 3 × ULN or > 3 × baseline if baseline > ULN
Creatinine clearance (ml/min/ 1.73 m ²)	< 30 < 60
Albumin (g/L)	< 30 < 20
Calcium (mmol/L)	< 2.0 < 1.75 > 2.9 > 3.1
Potassium (mmol/L)	< 3.2 < 3.0 > 5.5 > 6.0
Sodium (mmol/L)	< 130 > 150

Laboratory parameter	Criteria for marked laboratory abnormalities
	> 155
Chloride (mmol/L)	< 74 > 131
Creatine kinase (µg/L)	> 5 × ULN > 10 × ULN
Gamma-glutamyl transferase (U/L)	> 2.5 × ULN > 5 × ULN
Blood urea nitrogen (mmol/L)	> 2.5 × ULN > 5 × ULN
Uric acid (µmol/L)	> 590 > 720
Glucose (mmol/L)	< 3 < 2.2 > 8.9 > 13.9
TSH (mIU/L)	< 0.28 > 6.6
Free T ₃ (pmol/L)	< 2.8 > 7.8
Total T ₃ (nmol/L)	< 0.9 > 3.6
Free T ₄ (pmol/L)	< 7.2 > 24
Total T ₄ (nmol/L)	< 53 > 210
Triglycerides	> 5.7 mmol/L
Total cholesterol	> 2 × ULN

ALT = alanine aminotransferase; AST = aspartate aminotransferase; SI = standard international;
 TSH = thyroid-stimulating hormone; T₃ = triiodothyronine; T₄ = thyroxine; ULN = upper limit of normal.

Elevated liver parameters during DB study treatment will be summarized: the number (%) of subjects meeting the criteria defined below within a given central laboratory sample will be tabulated by treatment group. Percentages will be based on the number of subjects at risk, i.e., those having at least one post-baseline value for all parameters within the given criteria.

- AST or ALT > 3 × upper limit of normal (ULN)
- AST or ALT > 5 × ULN
- AST or ALT > 10 × ULN

- $TBIL > 1.5 \times ULN$ and $> 2 \times ULN$
- $ALP > 1.5 \times ULN$
- $(ALT \text{ or } AST > 3 \times ULN)$ and $(TBIL > 1.5 \times ULN)$
- $(ALT \text{ or } AST > 3 \times ULN)$ and $(TBIL > 2 \times ULN)$

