15. Known hypersensitivity or contraindication to drugs of the same class as the study treatment or to any excipients of the study drug formulation.
16. Not able or willing to stop treatment with moderate or strong CYP3A4 inhibitors, or treatment with moderate or strong CYP3A4 inducers, within at least 1 week prior to Visit 2.
17. Not able or willing to stop consumption of grapefruit, Seville (bitter) oranges or juices from those fruits within at least 1 week prior to Visit 2.

Criteria assessed at PSG visit between Visit 1 and Visit 2

18. Periodic limb movement disorder with arousal index (PLMAI) ≥ 15 /h (assessed on the 1st PSG night), restless legs syndrome, circadian rhythm disorder, REM behavior disorder, or narcolepsy.
19. Apnea/hypopnea index (AHI) ≥ 15 /h according to American Academy of Sleep Medicine criteria or event associated with blood oxygen saturation level by pulse oximetry (SpO₂) $< 80\%$, as assessed on the 1st PSG night.

Criteria assessed at Visit 1 and Visit 3

20. AST and/or ALT $> 2 \times$ ULN and/or direct bilirubin $> 1.5 \times$ ULN.
21. Severe renal impairment: known or defined as estimated creatinine clearance < 30 mL/min/1.73m², according to the 4-variable Modification of Diet in Renal Disease formula.
22. Hematology or biochemistry test results deviating from the normal range to a clinically relevant extent as per judgment of the investigator.
23. Any of the following conditions related to ECG abnormalities:
 - A prolonged QT interval corrected with Bazett's formula (QTcB) or QT interval corrected with Fridericia's formula (QTcF) (greater than 450 ms). If QTcB or QTcF is greater than 450 ms on the first ECG, a second ECG recording will be performed after at least 30 min. If QTcB or QTcF is greater than 450 ms on the second ECG, the subject is not eligible.

- A history of additional risk factors for torsade de pointes (e.g., heart failure, hypokalemia, family history of long QT syndrome).
- ECG with clinically significant atrioventricular (AV) conduction disturbance (e.g., second- or third-degree AV block), sick sinus syndrome, bradycardia (resting pulse < 40 bpm), or accessory bypass tract (e.g., Wolff-Parkinson-White).

Criterion assessed at Visit 1, Visit 2, Visit 3 and Visit 4

24. Any of the following conditions related to suicidality:

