7.4 Electrocardiography

Unless noted otherwise, ECG summaries and listings will include scheduled, re-test and unscheduled assessments.

Descriptive summary statistics for each scheduled visit (re-test excluded) will be provided for observed values and change from baseline in ECG parameters (QT corrected according to Fridericia's formula, QT corrected according to Bazett's formula, heart rate, PR, QRS).

Marked ECG abnormalities are defined in [Table 5](#). The following summaries will be provided for each ECG parameter:

- Number (%) of subjects with a marked ECG abnormality during the DB study period.
- Number (%) of subjects with a marked ECG abnormality during the treatment withdrawal period (based on the TWS).

Percentages will be based on the number of subjects at risk, i.e., those having at least one post-baseline value in the study period under consideration per ECG parameter for criteria based on post-baseline values only, or those having a baseline value and at least one post-baseline value in the study period under consideration per ECG parameter for criteria based on change from baseline. For non-mutually exclusive criteria (i.e., HR, PR, and QRS), a subject will be counted only once in case of multiple occurrences but may be reported in more than one marked ECG abnormality criterion of a given parameter. For mutually exclusive criteria (i.e., QTc), only the subject's worst post-baseline value (or worst change from baseline value) will be counted.

ECG findings during the DB study period and during the treatment withdrawal period (based on the TWS) will be summarized separately and listed. ECG abnormality categories and findings will be sorted by descending frequency, first in the highest ACT-541468 dose level, then in the next highest ACT-541468 dose level, and finally in the placebo treatment group. After this sorting, ECG abnormality categories will be presented in alphabetical order with ECG finding sorted within ECG abnormality category in alphabetical order. All ECG values for subjects with at least one marked ECG abnormality during the DB study period or during the treatment withdrawal period will be listed.

Table 5 **Marked abnormalities in ECG parameters**

ECG parameter	Criteria for marked ECG abnormalities
QTcF, QTcB (ms)	> 450 and \leq 480 > 480 and \leq 500 > 500 > 30 and \leq 60 increase from baseline > 60 increase from baseline
HR (bpm)	< 45 < 50 > 10 and \leq 20 decrease from baseline > 20 decrease from baseline
PR (ms)	> 200

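### For absolute criteria such as creatinine clearance < 60, the marked-abnormality tables count pre-existing and new cases together, which dilutes the risk ratio against placebo

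*SAP*

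**What the plan says.** SAP 7.3 sets the numerator: "The number (%) of subjects with marked laboratory abnormalities during DB study treatment will be tabulated". The denominator follows: "Percentages will be based on the number of subjects at risk, i.e., those having at least one post-baseline value for a given parameter". Neither depends on whether the subject already met the criterion at baseline.

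Table 4 of the SAP gives two creatinine clearance rows, < 30 and < 60 mL/min/1.73 m², both absolute. Protocol 4.4, criterion 21, excludes only the lower range: "Severe renal impairment: known or defined as estimated creatinine clearance < 30" mL/min/1.73 m². Criterion 22 adds a discretionary exclusion with no numeric limit: "Hematology or biochemistry test results deviating from the normal range to a clinically relevant extent as per judgment of the investigator".

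SAP 7.4 uses the same kind of denominator for its absolute criteria: "those having at least one post-baseline value in the study period under consideration per ECG parameter for criteria based on post-baseline values only". Table 5 includes PR > 200 ms, QRS > 110 ms and HR < 45 and < 50 bpm. Criterion 23 sets no PR or QRS limit and excludes resting pulse only below 40.

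Some rows do take account of baseline. In Table 4, the creatinine and high-hemoglobin criteria become relative to baseline when the baseline value exceeds the upper limit of normal.

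**The concern.** A reader of a table of marked abnormalities during treatment will usually take the percentages as a measure of what happened on treatment. For an absolute criterion that eligible subjects can already meet, part of the count is simply who was enrolled. Protocol 3.1 plans about 40% of subjects aged 65 or over, so clearance between 30 and 59 at entry may not be negligible, although the documents give no prevalence.

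At stake is how clearly the table shows a laboratory or ECG effect. Carried-over cases raise the percentage in every arm, pull the risk ratio towards 1 and add sampling noise. Elsewhere the SAP separates new from pre-existing: treatment-emergent adverse events must begin or worsen after treatment starts (7.2), and the suicidality scale is given a shift from baseline (7.9). The shift tables in 7.3 cover liver, thyroid, lipid and some hematology parameters but no renal parameter. No planned table counts how many subjects newly crossed the < 60 threshold.

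**Working it through.** The documents give no figure for this table, so there is none to reproduce. The check has two parts.

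**1. Which rows can contain eligible baseline cases?**

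| Criterion | Entry rule (Protocol 4.4) | Baseline cases possible? |
|---|---|---|
| Clearance < 60 | only < 30 excluded (21) | yes, 30 to 59, subject to investigator judgment (22) |
| Clearance < 30 | < 30 excluded (21) | essentially none |
| ALT/AST > 3 × ULN | > 2 × ULN excluded (20) | largely none |
| Creatinine; high hemoglobin | – | handled by baseline-relative wording in Table 4 |
| PR > 200, QRS > 110 | no numeric limit (23) | yes |
| HR < 50 | resting pulse < 40 excluded (23) | yes, 40 to 49 |

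**2. How much dilution follows for the < 60 row?**

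Let p be the share already meeting the criterion at baseline, s the share of these who also meet it on treatment (taken as equal across arms), and q the new-onset rate among the rest.

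- Tabulated rate = p·s + (1 − p)·q
- Tabulated difference = (1 − p)·(q_active − q_placebo), since the p·s term cancels
- Carried-over share of the placebo count = p·s / [p·s + (1 − p)·q_placebo]

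All inputs are assumptions: q = 2% on placebo and 6% on active, s = 1, and p from 1% to 20%. Among subjects not meeting the criterion at baseline, the ratio is 6/2 = 3.0 and the difference 4.0 points.

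| p | Placebo | Active | Ratio | Difference (points) | Carried-over share, placebo |
|---|---|---|---|---|---|
| 1% | 0.01 + 0.99 × 0.02 = 2.98% | 0.01 + 0.99 × 0.06 = 6.94% | 2.33 | 3.96 | 34% |
| 5% | 0.05 + 0.95 × 0.02 = 6.9% | 0.05 + 0.95 × 0.06 = 10.7% | 1.55 | 3.8 | 72% |
| 10% | 0.10 + 0.90 × 0.02 = 11.8% | 0.10 + 0.90 × 0.06 = 15.4% | 1.31 | 3.6 | 85% |
| 20% | 0.20 + 0.80 × 0.02 = 21.6% | 0.20 + 0.80 × 0.06 = 24.8% | 1.15 | 3.2 | 93% |

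With s = 0.8 the ratios are 2.42, 1.64, 1.37 and 1.18, and the differences are unchanged. With new-onset rates of 3% and 9% and s = 1, the ratios are 2.50, 1.73, 1.43 and 1.21. The ratio is thus sensitive to even a small pre-existing share; the difference loses only that share.

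**The case against.** The strongest reply is that counting any on-treatment occurrence against a randomized placebo arm is a legitimate convention. The protocol endpoint (6.5) concerns marked abnormalities on treatment and does not say new or treatment-emergent. That stands, and it is why the planned count should be kept.

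A reader might infer that pre-existing values mask drug effects. The documents do not support this. Allocation is randomized and stratified by age, so carriers are expected to balance and the contrast shrinks without reversing. Change from baseline is summarized for all hematology and chemistry parameters and for the ECG parameters. Heart rate also has rows for decrease from baseline. All data of flagged subjects are listed, and clinically significant laboratory changes that are new or worsened are adverse events (Protocol 9.1.1). These outputs help only in part: average change does not count threshold crossings, and listings give no between-arm comparison.

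A reader might also infer that all marked-abnormality rows are affected. They are not, as the first table shows. Criterion 22 may also remove some subjects with clearance of 30 to 59.

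Finally, a reader might translate the dilution into lost power. With 300 per arm and 10% pre-existing, a two-sided 5% comparison under the assumed rates has power of about 0.25, against 0.66 when restricted to subjects not meeting the criterion at baseline. The arithmetic is sound, but no test is planned on these tables, so this is not an operating characteristic of the study.

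**Conclusion.** The point holds as a minor one. The clearance < 60 row, and PR > 200, QRS > 110 and HR < 50 in the ECG table, mix pre-existing with new cases, and no planned table separates them. Under the assumed rates the risk ratio of 3.0 falls to between 2.33 and 1.15 as the pre-existing share goes from 1% to 20%, while the difference falls from 4.0 points to between 3.96 and 3.2. These sizes rest on new-onset rates, persistence and prevalence that the documents do not give; no size is estimated for the ECG rows. Creatinine, high hemoglobin, clearance < 30 and ALT/AST are largely or wholly unaffected. Sample size, alpha and the efficacy conclusions do not change.

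**What to change.** In SAP 7.3, and for the absolute criteria in 7.4:

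- Keep the planned count of any on-treatment occurrence.
- For each absolute criterion, add the number (%) of subjects newly meeting it, with numerator and denominator limited to subjects who have a baseline value not meeting that criterion.
- Report separately the subjects who met it at baseline, showing any who worsened, and those without a baseline value. Replacing the planned count with the restricted one would take worsening from an abnormal baseline out of the tabulated rate; adding to it avoids that.
- Add creatinine clearance to the shift tables.

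All of this uses data already collected and follows the logic of the SAP's own baseline-relative rows. The cost is a few more table rows and denominators that differ by criterion.

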7.4 Electrocardiography

Unless noted otherwise, ECG summaries and listings will include scheduled, re-test and unscheduled assessments.

Descriptive summary statistics for each scheduled visit (re-test excluded) will be provided for observed values and change from baseline in ECG parameters (QT corrected according to Fridericia's formula, QT corrected according to Bazett's formula, heart rate, PR, QRS).

Marked ECG abnormalities are defined in [Table 5](#). The following summaries will be provided for each ECG parameter:

- Number (%) of subjects with a marked ECG abnormality during the DB study period.
- Number (%) of subjects with a marked ECG abnormality during the treatment withdrawal period (based on the TWS).

Percentages will be based on the number of subjects at risk, i.e., those having at least one post-baseline value in the study period under consideration per ECG parameter for criteria based on post-baseline values only, or those having a baseline value and at least one post-baseline value in the study period under consideration per ECG parameter for criteria based on change from baseline. For non-mutually exclusive criteria (i.e., HR, PR, and QRS), a subject will be counted only once in case of multiple occurrences but may be reported in more than one marked ECG abnormality criterion of a given parameter. For mutually exclusive criteria (i.e., QTc), only the subject's worst post-baseline value (or worst change from baseline value) will be counted.

ECG findings during the DB study period and during the treatment withdrawal period (based on the TWS) will be summarized separately and listed. ECG abnormality categories and findings will be sorted by descending frequency, first in the highest ACT-541468 dose level, then in the next highest ACT-541468 dose level, and finally in the placebo treatment group. After this sorting, ECG abnormality categories will be presented in alphabetical order with ECG finding sorted within ECG abnormality category in alphabetical order. All ECG values for subjects with at least one marked ECG abnormality during the DB study period or during the treatment withdrawal period will be listed.

Table 5 **Marked abnormalities in ECG parameters**

ECG parameter	Criteria for marked ECG abnormalities
QTcF, QTcB (ms)	> 450 and \leq 480 > 480 and \leq 500 > 500 > 30 and \leq 60 increase from baseline > 60 increase from baseline
HR (bpm)	< 45 < 50 > 10 and \leq 20 decrease from baseline > 20 decrease from baseline
PR (ms)	> 200
QRS (ms)	> 110

bpm = beats per minute; ECG = electrocardiogram; HR = heart rate; QTcB = QT interval corrected according to Bazett's formula; QTcF = QT interval corrected according to Fridericia's formula.

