7.2.3.12 ECG assessment

A standard 12-lead ECG is to be performed at Visit 1, in the second morning of Visit 3, Visit 8 and at Visit 10.

12-lead ECG will be recorded at rest with the subject in the supine position. Data records will be sent to the evaluation center for central reading.

Details will be provided in the 12-lead ECG laboratory manual.

The following parameters will be evaluated: PQ or PR (ms), QRS (ms), QT (ms), heart rate (HR; bpm), and rhythm. QTc (ms) will be calculated according to:

- Bazett's formula: $QTcB = QT / (RR)^{1/2}$
and
- Fridericia's formula: $QTcF = QT / (RR)^{1/3}$, where $RR = 60 / HR$

If the central review of the ECG detects a prolonged QTcB and/or QTcF interval greater than 450 ms for a subject at screening (Visit 1 or Visit 3), the ECG must be repeated (at least 30 min after first ECG). If the central review confirms that the repeated ECG shows

a QTcB and/or QTcF interval greater than 450 ms, the subject cannot be enrolled into the study.

Clinically significant findings detected after signing of ICF which meet the definition of an AE must be recorded in the eCRF.

ECG data collected by the CRO will be electronically transferred to Idorsia.

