7 SAFETY VARIABLES AND ANALYSES

7.1 Overview of safety analyses including subgroup analyses

Unless noted otherwise, the SS will be used for tables and listings of safety data.

Safety data described below will be listed.

In the event of permanent study treatment discontinuation, it is recommended to perform the safety assessments of Visit 8 within 7 days of the last DB study treatment intake. Although some subjects may be considered as being off study treatment, the time from the

last DB study treatment intake to the Visit 8 assessments is expected to be short. Therefore, for subjects who prematurely discontinue treatment, the safety data (laboratory tests, ECG, vital signs) measured within 7 days of the last DB study treatment intake will be included as being taken during DB study treatment. A subject who prematurely discontinues treatment may continue the planned study visits until EOS, without the run-out period. Therefore, for subjects who prematurely discontinue treatment, the safety data (laboratory tests, ECG, vital signs) measured more than 7 days from the last DB study treatment intake will be excluded from analyses.

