12.2 Study periods

The Screening period is defined as the time from the informed consent date until one day before the Run-in period start date.

The Run-in period is defined as the time from the start of the run-in single-blind placebo treatment to one day before start of DB study treatment or, for those not starting DB study treatment, to run-in single-blind placebo treatment end date.

The DB study period is defined as the time from the day of DB study treatment start until the day of EODBT (Visit 8, 2nd morning), or, for those who prematurely discontinued DB study treatment (i.e., those without an EODBT date), until one day after DB study treatment end date (if the treatment is taken before midnight) or the day of DB study treatment end date (if the treatment is taken after midnight). Time of treatment intake between 00:00 and 11:59 is considered as 'after midnight', while a time between 12:00 and 23:59 is considered as 'before midnight'. For any missing or incomplete time, it is presumed that the treatment was taken before midnight. For subjects who complete DB study treatment with an

interruption before continuing the run-out single-blind placebo treatment, the end of DB study period is the run-out single-blind placebo treatment start date – 1 day.

For those subjects in the TWS, the treatment withdrawal period (or Run-out period) is defined as the time from one day after the end of the DB study period to the latter of seven days after the end of the DB study period or Visit 10 date.

The safety follow-up period is defined as the time from one day after the end of the treatment withdrawal period for those starting the treatment withdrawal period (i.e., subjects in the TWS) until EOS date; or from one day after the end of the DB study period for those not starting the treatment withdrawal period until EOS date.

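### SAP 7.1 and SAP 7.4/12.2 set different cut-offs for ECGs in subjects who stop double-blind treatment early (7 days versus 0 to 1 day), so the marked-ECG table can be built in two ways

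*SAP*

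**What the plan says.** **SAP 7.1** covers subjects who permanently stop DB treatment early. Their laboratory, ECG and vital-sign data "measured within 7 days of the last DB study treatment intake will be included as being taken during DB study treatment". Data "measured more than 7 days from the last DB study treatment intake will be excluded from analyses".

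**SAP 7.4** names a different window. It tabulates the "Number (%) of subjects with a marked ECG abnormality during the DB study period", with percentages based on "those having at least one post-baseline value in the study period under consideration". The summary of ECG findings and the trigger for listing all of a subject's ECG values are also tied to the DB study period or the treatment withdrawal period.

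**SAP 12.2** defines the DB study period. For early stoppers it runs "until one day after DB study treatment end date (if the treatment is taken before midnight"), or to "the day of DB study treatment end date (if the treatment is taken after midnight"). Safety follow-up then runs "from one day after the end of the DB study period for those not starting the treatment withdrawal period until EOS date". No exception is made for the 7-day rule in 7.1.

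**Protocol 7.2.3.12** gives the ECG schedule: "A standard 12-lead ECG is to be performed at Visit 1, in the second morning of Visit 3, Visit 8 and at Visit 10". Protocol 5.1.9 and the footnotes to Protocol Table 1 say that early stoppers are recommended to have the Visit 8 safety assessments within a week of the last dose, and that they do not do Visits 9 and 10.

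**Protocol 10.3.3** describes the same marked-ECG table as covering DB study treatment, which is the wording of SAP 7.1 and not that of SAP 7.4.

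**The concern.** One count has two stated limits. SAP 7.1 decides that an ECG taken up to a week after stopping is close enough to treatment to count. SAP 7.4, combined with SAP 12.2, applies a limit of at most one day. Two programmers could each follow the SAP and produce different tables.

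The ECG table is more exposed than most because the schedule is thin: Visit 8 is the only scheduled post-baseline ECG tied to DB treatment. For an early stopper, the stop-visit ECG will usually be the only scheduled one that SAP 7.1 admits. Some of these subjects will have stopped for an adverse event, so they are a group that one would not want to drop from a cardiac safety table by accident. Rows for the more extreme QTc categories are likely to hold few subjects, and one subject more or less would show.

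**Working it through.** The plan gives no figure on this point to reproduce. The check compares the two windows and then bounds the number of subjects between them.

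**1. Windows.** Day 0 is the calendar date of the last DB dose.

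| Day of ECG | SAP 7.1 | SAP 7.4 with 12.2, dose before midnight | SAP 7.4 with 12.2, dose after midnight |
|---|---|---|---|
| 0 | counted | counted | counted |
| 1 | counted | counted | not counted |
| 2 to 7 | counted | not counted | not counted |
| 8 or later | not counted | not counted | not counted |

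The rules disagree on 6 calendar days for a dose before midnight (days 2 to 7) and on 7 for a dose after midnight (days 1 to 7).

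**2. Where the disputed ECGs go.** Under SAP 12.2 they fall in safety follow-up. SAP 7.4 plans marked-abnormality tables only for the DB study period and the treatment withdrawal period. The second is based on the Treatment withdrawal set, which requires at least one run-out placebo dose (SAP 4.1.5). Early stoppers have no run-out, so that table does not recover them.

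**3. Effect on the table.** If the disputed ECG is the subject's only post-baseline ECG in the window, the at-risk definition in SAP 7.4 is not met. The subject then leaves numerator and denominator together.

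**4. How many.** The only stopping rate in the documents is in SAP 6.1.4: 14 of 356 subjects in a one-month Phase 2 study.

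- Rate: 14/356 = 3.93%.
- Per arm of 300 (Protocol 5.1.3): 300 × 14/356 = 11.8, about 12.
- Stops due to adverse events: 4/356 = 1.1%, so 300 × 4/356 = 3.4, about 3 per arm.

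The share of these with an ECG only in the disputed days depends on when the ECG is done, which is not documented:

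- all done the morning after the last dose: 0%, so 0 per arm;
- all done on day 2 or later: 100%, so up to about 12 per arm;
- even spread over days 1 to 7, dose before midnight (assumption): 6/7 = 86%, so 11.8 × 6/7 = 10.1 per arm;
- even spread over days 0 to 7, dose before midnight (assumption): 6/8 = 75%, so 11.8 × 0.75 = 8.9 per arm.

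The supportable range at the Phase 2 rate is therefore about 0 to 12 per arm. If the three-month rate were three times as high (assumption), the upper end would be 3 × 11.8 = 35.4, about 35 per arm.

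**5. What one subject does to a row.** As an illustration, suppose 300 subjects have an ECG, 12 of them fall out, and one of the 12 is the only subject in a row. The row changes from 1/300 = 0.3% to 0/288 = 0%.

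**6. Laboratory data.** In SAP 7.3 the marked-abnormality table uses the SAP 7.1 wording and has no conflict. The row for change from baseline to last value uses the DB study period and does. The effect there is milder: a subject with an earlier scheduled sample (Visit 6 or 7, Protocol 7.2.5.1) stays in the row, but with an older value.

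**The case against.** The strongest answer is that SAP 7.1 governs. It opens the safety section, names ECG, addresses exactly these subjects, and sets its own upper limit. SAP 12.2 is a general definition that also serves adverse events and concomitant therapy. A specific rule would normally override a general one, and otherwise 7.1 would have no effect on the marked-ECG table. Protocol 10.3.3 points the same way. This argument stands to the extent that the loss is conditional on how the table is programmed.

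It does not remove the conflict. Nothing says that 7.1 overrides 12.2. SAP 2 sends the reader to 12.2 for the detailed period definitions. Where a section-specific assignment was wanted it was written out, as SAP 7.9 does for the suicidality scale. SAP 13 lists no change to the ECG analysis that would explain why 7.4 departs from the protocol's term.

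A reader might go further and infer that most early stoppers' only on-treatment ECG is lost. The documents do not support this:

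- *Most* needs ECG timing, which is not given. An ECG on the morning after the last dose counts under both rules.
- *Only* holds for scheduled ECGs at best. SAP 7.4 also includes re-test and unscheduled ECGs. Early stoppers who stay in the study also keep the planned Visit 8, although SAP 7.1 would exclude that ECG if it came after day 7.
- Multiplying the Phase 2 rate for three months runs against SAP 6.1.4, which expects only a slightly higher rate of intercurrent events. Two of the 14 Phase 2 stops were consent withdrawals, and such subjects would contribute no later ECG if consent to the study had ended. Without them the upper figure is 300 × 12/356 = 10.1 per arm.

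Two further points stand. Because subjects leave numerator and denominator together, a percentage is biased only if their abnormality rate differs from that of the others. And the tables are descriptive: the by-visit ECG statistics do not depend on the DB study period, and SAP 7.1 says that safety data will be listed.

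**Conclusion.** The conflict is real and needs no assumption to see: SAP 7.1 gives 7 days, while SAP 7.4 with 12.2 gives 0 to 1 day, for the same ECGs in the same subjects. Read literally, ECGs on days 2 to 7 (days 1 to 7 after an after-midnight dose) drop out of the marked-abnormality counts, the at-risk denominator, the findings summary and the listing trigger.

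The number of subjects cannot be derived. It lies between zero and all early stoppers with such an ECG. The 12-per-arm upper figure assumes that the one-month rate carries over, that every early stopper has the ECG, and that none is done early enough to satisfy both rules. The documents do not establish that the loss will occur, or that it would affect a majority.

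No hypothesis test is touched. It is a modest inconsistency in a safety table, worth settling before unblinding so that the choice of window cannot depend on the results.

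**What to change.** In SAP 7.4, replace the reference to the DB study period with: *during DB study treatment (for subjects who prematurely discontinue, up to 7 days after last DB intake, as in Section 7.1)*. Apply it to the marked-abnormality counts, the at-risk denominator, the ECG findings and the listing. This brings the table back to the term used in Protocol 10.3.3. Apply the same window to the last-value row in SAP 7.3.

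Leave the period definition in SAP 12.2 as it is. Adverse-event tables use it and safety follow-up starts from it, so extending it there would make the two periods overlap.

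The cost is a few words in two sections and no new data. The downside is that a few values taken shortly off drug are counted as on treatment, which SAP 7.1 already accepts.
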